IV. Project Design and Procedures.

- a. Performance Measurement.** The primary outcome is UTI within 14 +/- 2 days post-surgery. A UTI is defined as an infection in any part of your urinary system which may include the kidneys, ureters, bladder, and urethra. Most infections involve the lower urinary tract (bladder and urethra), and are treatable with antibiotics. If a UTI spreads to the kidney, it can become a more serious complication. Women are at a greater risk of developing a UTI than men are. Pre-operative antibiotics will be collected to determine if this directly affects the outcome of a UTI. Visits to the ED for urinary pain, incontinence, or fever will also be followed for determination of UTI. Participants will provide a urine sample 0-24 hours before surgery. The sample will be tested with a rapid urine analysis (UA) test. This measure was chosen so that study UAs results are not to be confused with standard UAs conducted with samples collected after catheter placement. Participants will be followed up by research staff ~24 hours post-surgery for a second UA test. A third UA will be conducted at the patients' post-op check. At follow-up visits, participants will also

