be assessed for symptoms of UTI since surgery by assessment of: urethral discomfort, suprapubic tenderness or pelvic pain, sense of urinary urgency, frequency or dysuria, fever, antibiotic use, and clinical and laboratory data suggesting infection (UA with +leukocyte esterase +/- nitrates, urine culture with $>10^5$ bacterial colony forming units per mL (CFU)). Asymptomatic bacteriuria will be considered a UTI for this study (defined as $>10^5$ CFU/mL on urine culture). Patients who are treated with antibiotics for UTI without laboratory data suggesting infection will be included in UTI group. For participants reporting ED visits prior to 14 +/- 2 day visit, ED reports will be obtained and an assessment will be made regarding the symptomatic UTI diagnosis. Those meeting these criteria will be followed with symptom and laboratory analysis. All positive UA test will be confirmed by laboratory analysis for final diagnosis. Results of +leukocyte esterase +/- nitrites will be considered abnormal. If a diagnosis of UTI does not exist in the patient chart outside of study, the patient's clinical picture will be evaluated independently by 2 separate care providers to determine if meeting criteria for UTI (symptomatic bacteriuria as defined above). If there is discrepancy a third provider will be the determining opinion. Participants meeting the primary endpoint (UTI) will be discontinued from the study following.

Secondary outcomes include: hospital length of stay, readmissions, antibiotic use at the time of surgery and post-surgery. Measures of UTI, and secondary outcomes will be collected from observation during study visits and from the patient medical charts., If closed drainage system was disrupted during placement (to back fill bladder intra-operatively), and method of catheter discontinuation ("fill and pull" versus "pull and void" methods) will be collected for comparison between the groups for analysis as a possible confounding variables.

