c. Study Design and Research Method. We will conduct a single-site Randomized Control Trial (RCT) in order to examine the use of an aseptic protocol for catheter insertion during gynecologic oncology surgeries for quality improvement. This study will take place at the UCH inpatient surgical unit of gynecologic oncology. The catheter protocol for QI will be conducted in the operating room prior to surgery and will not increase prep time or operating room time. Follow-up will be conducted during standard outpatient care visits and will also not increase clinic use time.

The intervention in this study is a controlled aseptic pre-treatment protocol for catheter use in the operating room involving dipping the tip of the catheter into betadine prior to insertion and maintaining catheter in the sterile plastic sleeve during preparation, insertion and post-operatively to avoid excess exposure to the environment. The Physician performing the operation will be responsible for inserting the catheter. Patients with normal UA pre-surgery will be randomized 1:1 to one of two arms prior to surgery:

- 1) Aseptic protocol for catheter insertion using betadine treated catheter and maintaining plastic sleeve on catheter *or*
- 2) SOC catheter insertion in which catheter is inserted right out of package/non-treated catheter.

Prior to study initiation, the PI will train providers on the proper use of the protocol. Catheter insertion procedures will be documented in the operation note following surgery. Compliance will be measured by adherence to both betadine use and maintenance of plastic sleeve. Standard of care practices for infection control are to be conducted by providers on all participants. This includes: hand hygiene, inserting catheters for appropriate indications, remove catheters when no longer needed, maintain a close system keeping bag and tubing below the bladder.

We will collect general patient demographics to assure similarities between the randomized groups. These will include age, race/ethnicity, BMI, insurance type, diagnosis (reason for surgery), history of diabetes, menopausal status, and smoking status. MRN data will be collected in order to pull data directly into the OnCore data management system.

d. Study Procedures

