Additionally, there is and will remain practice variations in catheter placement. While we hope to find a difference despite these differences, it is possible that the intervention may give a false impression of improvement simply by focusing attention on a protocol. While it is difficult to remove confounding from any study, randomization and analysis adjustments will be used to reduce as much as possible.

VI. Data Analysis Plan:

This study will assess a population of patients undergoing extended surgery requiring catheter placement to be performed by the Gynecologic Oncology service. De-identified patient data will be collected into OnCore and exported to SPSS for data analysis. Initial summary statistics will be performed to report the distribution of the data, including variable means, medians, proportions and missing data.

An intent-to-treat analysis will be conducted. All participants receiving treatment per protocol will be included in the final analysis. If there are any participants who are randomized but do not receive the intended treatment, we will document the reasons for their being withheld treatment.

For the primary outcome measure of UTI rate at each of the time points (24 hours and 14 +/- 2 days), we will perform a test of binomial proportions for testing the null hypothesis of no difference between the treatment arms. Because we are performing tests at two time points, we will adjust for the multiple comparisons using Bonferroni's method.

We will also explore the association between treatment arms and other covariates (symptomatic and demographics factors) using bivariate methods. The particular analysis method for testing the association between them will depend on the distribution of the covariates. For example, symptomatic presentation variables (fever, pelvic pain, sense of urgency or dysuria, and antibiotic use) are categorical, and their association with treatment arm will be evaluated with a chi-square statistic.

For demographic variables, Student's *t*-test (for continuous variables) and chi-square tests (for categorical variables) will be used to compare the two treatment arms. Variables found to be significant in these bivariate analyses will be included in multivariable analysis using logistic regression. Logistic regression models will be used to identify significant independent predictors associated with UTI

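### No masking to arm is specified for the providers who adjudicate UTI, so the primary endpoint can be classified differently in the two arms

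*Combined protocol and SAP*

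**What the plan says.** Section IV.a sets the endpoint: "The primary outcome is UTI within 14 +/- 2 days post-surgery". A patient can be counted as a case in several ways:

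- a UTI diagnosis already in the chart;
- a urine culture above 10^5 CFU/mL, with or without symptoms;
- antibiotic treatment alone: "Patients who are treated with antibiotics for UTI without laboratory data suggesting infection will be included in UTI group";
- adjudication, which is reserved for patients with no charted diagnosis made elsewhere. Their "clinical picture will be evaluated independently by 2 separate care providers to determine if meeting criteria for UTI", and the criterion given in parentheses is symptomatic bacteriuria. For ties, "If there is discrepancy a third provider will be the determining opinion".

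The same section has a laboratory safeguard: "All positive UA test will be confirmed by laboratory analysis for final diagnosis". Section IV.e adds that confirming a UTI would also use urine culture.

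On visibility of the arm, section IV.c makes the operating physician responsible for inserting the catheter and says "Catheter insertion procedures will be documented in the operation note following surgery". Section IV.e keeps the plastic cover on for as long as the catheter is in place in the intervention arm. Section III counts five providers to be trained. No section mentions blinding or masking of patients, operators, assessors or adjudicators.

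**The concern.** The only safeguard named for adjudication is that the two providers work independently. In context that means independently of each other. It does not mean without knowledge of the allocation. The surgeon cannot be masked, the chart records how the catheter was inserted, and the study hypothesis has a direction. An adjudicator who knows the arm may read the same urgency, pelvic discomfort or borderline urine result differently in the two arms.

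Randomization does not protect against this, because the error arises after allocation. Covariate adjustment does not help either, because the error is in the outcome. Section V names randomization and analysis adjustments as its defences against confounding, and neither corrects outcome misclassification that differs by arm.

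**Working it through.** **1. The plan's own figure.** Inputs from section IV.b: 40% against 20%, alpha 0.05, power 0.84. Two-sidedness is assumed because the plan does not state it.

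- n0 = [1.960·√(2·0.30·0.70) + 0.994·√(0.40·0.60 + 0.20·0.80)]² / 0.20² = 90.2.
- With continuity correction, n = (n0/4)·[1 + √(1 + 4/(n0·0.20))]² = 99.9, or 100 per arm.

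The stated sample size reproduces. Masking adjudicators changes neither it nor the power.

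**2. How much discretion adjudicators have.** Two readings are possible.

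- *Strict:* a culture above 10^5 CFU/mL already makes the patient a case, and a patient without one cannot meet symptomatic bacteriuria. Adjudicators then decide very little.
- *Looser:* they weigh a clinical picture against criteria defined earlier in the section. That earlier text lists symptoms, fever, antibiotic use, dipstick results and culture together, with no rule for combining them. The adjudication criterion also says symptomatic, although asymptomatic bacteriuria counts as UTI elsewhere in the section.

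The wording does not settle which reading applies, so some discretion remains. The plan does not say what share of patients would be adjudicated.

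**3. Illustration: over-calling in the standard-of-care (SOC) arm.** Assume no true effect, the protocol's 40% rate in both arms and 100 per arm. A proportion q of SOC non-cases is upgraded. The values of q are assumptions and have no source in the documents.

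- Observed SOC rate = 0.40 + 0.60·q. The intervention arm stays at 0.40.
- Test: z = (difference in observed proportions) / √(2·p̄(1−p̄)/100), two-sided, with p̄ the pooled proportion. The rejection probability is summed exactly over both binomial distributions.

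| q | SOC observed | Type I error at 0.05 | at 0.025 |
|---|---|---|---|
| 0 | 40% | 5.1% | 2.5% |
| 5% | 43% | 7.5% | 4.0% |
| 10% | 46% | 14.4% | 8.8% |
| 15% | 49% | 26.1% | 17.7% |

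The 0.025 column is the Bonferroni level for the two time points in section VI if the total is 0.05.

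**4. Illustration: under-calling in the intervention arm.** A share f of UTIs depends on judgement, and an extra proportion m of those is missed in the intervention arm only. Its observed rate is 0.40·(1 − f·m), against 40% in the SOC arm. The table gives the chance of a false significant result favouring the intervention.

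| f | m | Intervention observed | At 0.05 (unbiased 2.6%) | At 0.025 (unbiased 1.3%) |
|---|---|---|---|---|
| 25% | 20% | 38% | 4.8% | 2.6% |
| 50% | 20% | 36% | 8.4% | 4.8% |
| 50% | 30% | 34% | 13.9% | 8.6% |
| 100% | 30% | 28% | 43.5% | 32.7% |

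Both models behave alike: the effect is small when little depends on judgement and large when much does.

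**The case against.** The best defence is that the endpoint is anchored in the laboratory. Positive dipsticks go for confirmation, the adjudication criterion requires bacteriuria, and a qualifying culture makes a case whatever anyone thinks of the symptoms. On the strict reading, adjudicators could hardly upgrade a true non-case. Small distortions also matter little: upgrading 1% to 3% of SOC non-cases at a 40% rate gives a type I error of only 5.3% to 6.0% at 0.05. This stands as a limit on the size. It does not remove the gap, because the text also invites a judgement on the clinical picture.

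A second objection is that adjudication may not be the most subjective route. Chart diagnoses and antibiotic treatment without laboratory data also come from clinicians who may know the arm. That is right, and it means masking adjudicators is only part of the remedy.

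A reader might also draw stronger conclusions that the documents do not support:

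- *That adjudicators are known to be unmasked, or the trial is declared open-label.* Neither is stated. Masking is simply not specified.
- *That adjudicators read the operation note, or are drawn from the five trained providers.* The plan describes neither their material nor who they are. It only fails to rule these out.
- *That section V concedes this bias.* Its remark that "it is possible that the intervention may give a false impression of improvement simply by focusing attention on a protocol" follows a sentence on variation in catheter placement. It describes an effect of attention and does not mention biased classification of outcomes.

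**Conclusion.** The point holds as a gap in the design of endpoint ascertainment. Masking of adjudicators is not specified, the arm is discoverable, and the patient's own surgeon is not excluded. The primary endpoint can therefore be biased. Bias toward the intervention is plausible given the directional hypothesis, but the documents do not establish it.

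The magnitude is unknown. The type I error figures of 7.5% to 26.1% at 0.05, and 4.0% to 17.7% at 0.025, rest on assumed upgrade rates of 5% to 15% in one arm and on the protocol's 40% rate. It is tempting to call them an upper bound, on the ground that only patients without a chart diagnosis are adjudicated. That does not follow: the modelled patients are non-cases, who would mostly have no chart diagnosis, so the restriction hardly limits them. The figures show sensitivity and are neither a bound nor a forecast.

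It would also be too strong to say that no analysis could help afterwards, since an analysis of culture-confirmed cases bypasses the adjudicators' judgement. Prevention is still better and cheap, so the change is worth making before adjudication starts.

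**What to change.** In section IV.a, state that all adjudicators, including the third, are masked to arm and did not operate on the patient. The coordinator should give them a packet of symptoms, temperature, urine analysis, culture, antibiotic use and ED notes, with the operation note and any mention of Betadine or the sleeve removed.

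In section VI, add a sensitivity analysis of the primary comparison limited to culture-confirmed UTI (above 10^5 CFU/mL), because masked adjudication leaves chart diagnoses and antibiotic-only cases exposed. This analysis does not correct for any difference between arms in who has a culture sent, and the report should say so.

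The cost is a little coordinator time for redaction. No extra staff are needed: if adjudicators come from the five providers, leaving out the operator leaves four, and at most three are required. Sample size, intervention and patient care are unchanged.

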Participants will conduct the following study visits over 2 weeks. All costs associated with routine standard of care procedures for catheter insertions and diagnosing and treatment of a UTI will be the responsibility of the patient and/or their insurance provider. All costs associated with procedures conducted for research only will be paid for by the research study.

- **Visit 1 Screening and Enrollment:** Potential participants will be screened and consented for study up to 30 days prior to their surgical procedure. Inclusion/Exclusion criteria will be reviewed at the time of consent and baseline data including physical exam, health history, clinical diagnosis and concomitant medications will be collected following consent. A urine sample will be collected and analyzed 0-24 hours prior to procedure.
- **Visit 2 Randomization and Catheter Insertion:** Participants will be randomized to either the SOC catheter protocol or catheter insertion including Betadine on the day of procedure. Standard protocol will be followed for catheter preparation and insertion. Any adverse events following insertion will be recorded. Pre-operative antibiotics will also be recorded.
- **Visit 3, 24-hour post-op:** Patients will be assessed at 24 hours post-op in-patient. A urine sample will be collected and analyzed. Any positive urine analysis will be further analyzed and confirmed by the UCH laboratory per SOC procedures. Patients will be assessed for symptomatic signs of UTI and review of AEs following procedure.

- **Visit 4; 2-week post op:** Patients will be assessed 2-weeks post-op at their SOC post-op clinic visit. A urine sample will be collected and analyzed. Any positive urine analysis will be further analyzed and confirmed by the UCH laboratory per SOC procedures. A physical exam will also be collected. Patients will be assessed for symptomatic signs of UTI and review of AEs and ED visits since the last visit. Data including hospital stay, readmission, and antibiotic use will be collected. Patient satisfaction with catheter procedure will also be collected. Patient will be finished with study following visit 4.

e. Description, risks, and justification of procedures and data collection tools:

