- Consent and randomization: Patients will be randomized to standard of care intraoperative catheter placement versus aseptic protocol for catheter insertion upon providing informed consent. Randomization will be performed using the REDCap randomization module and will be performed by the study coordinator or research manager.
- Urine analysis with urine dip: Patients will be asked to provide a clean catch urine sample in provided collection cup prior to surgery (done as standard of care), a catheter collected urine sample at 24hrs post-operatively (research procedure) and another clean catch specimen at their 2-week surgical follow-up (research procedure). This collection and analysis is low risk except for the possibility of unnecessary treatment if abnormal sample is obtained. Abnormal samples will be correlated with patient history/complaints and confirmed with formal urine analysis. Confirmation of UTI would also utilize urine culture. The urine analysis by dip gives a fast yet reliable indicator of urinary tract infections. Pre-operative/pre-randomization allows us to exclude patients who may have underlying UTI prior to initiation of the study.
- Catheter placement: The aseptic protocol involves dipping standard catheter in an aseptic betadine solution and leaving a pre-existing plastic cover in place over the catheter during insertion and while in place. We do not anticipate any added risk of the aseptic protocol to the patient although patients may experience some increased irritation due to the protective plastic cover.

Anticipated Risks

While the study anticipates minimal risks, the following outlines any potential minimum risk to subjects:

- i. **Breach of Confidentiality:** Data obtained using information from medical records poses minimal risk. All procedures in which information is being obtained will be conducted per standard of care. There is a risk that a patient's privacy may not be protected. This risk is uncommon.

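### Section IV.a gives two conflicting criteria for the primary endpoint: asymptomatic bacteriuria counts as a UTI, but the adjudicators are told to look for symptomatic bacteriuria

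*Combined protocol and SAP*

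**What the plan says.** The primary outcome in IV.a (Performance Measurement) is UTI within 14 +/- 2 days of surgery. The section lists symptoms, urinalysis findings and a culture threshold of more than 10^5 CFU/mL as things to assess. It then gives two inclusion rules:

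- "Asymptomatic bacteriuria will be considered a UTI for this study", defined by that culture threshold.
- "Patients who are treated with antibiotics for UTI without laboratory data suggesting infection will be included in UTI group".

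For emergency department visits, reports are obtained and "an assessment will be made regarding the symptomatic UTI diagnosis". On laboratory work it says "All positive UA test will be confirmed by laboratory analysis for final diagnosis".

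The adjudication rule comes next. It applies "If a diagnosis of UTI does not exist in the patient chart outside of study". Two providers then review the clinical picture independently "to determine if meeting criteria for UTI (symptomatic bacteriuria as defined above"), and a third decides if they differ.

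IV.d repeats the laboratory step for the 24-hour and 2-week visits: "Any positive urine analysis will be further analyzed and confirmed by the UCH laboratory per SOC procedures". IV.e says "Abnormal samples will be correlated with patient history/complaints and confirmed with formal urine analysis", and adds that culture is also used to confirm a UTI.

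**The concern.** The adjudication parenthesis and the two inclusion rules do not describe the same endpoint. The parenthesis also points back to a definition that is not there under that name: the only bacteriuria defined by name earlier in the section is the asymptomatic kind.

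This is the primary, binary outcome, so the sentence that is followed decides whether a patient is an event. The third provider does not help, because that person breaks ties under the same parenthesis. The classification also affects follow-up. IV.a takes participants out of the study once they reach the endpoint, so a disputed 24-hour case bears on whether the 2-week data in IV.d are collected.

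**Working it through.** No arithmetic decides this point. The check is to take patients with no UTI diagnosis in the outside chart, who are the ones that trigger adjudication, and apply each rule in IV.a.

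| Patient without an outside chart diagnosis | Inclusion rules in IV.a | Adjudication parenthesis, read literally |
|---|---|---|
| Symptoms, culture above 10^5 CFU/mL | UTI on the natural reading | UTI |
| No symptoms, culture above 10^5 CFU/mL | UTI | Not a UTI |
| Treated with antibiotics for UTI, no laboratory evidence | UTI | Not a UTI (no bacteriuria shown) |

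The second and third rows conflict.

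**Can the second row occur?** Yes. IV.e labels the 24-hour and 2-week urine samples as research procedures. A symptom-free woman whose positive dip and culture come only from one of these may have no diagnosis in the chart outside the study. She then goes to adjudication.

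**Is the term defined earlier?** Only in part. The symptom list and the culture threshold both precede the parenthesis. No rule says how many symptoms, or which combination of symptoms and laboratory findings, make up symptomatic bacteriuria, and the label itself is not used before.

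**Does another section settle it?** No. The laboratory-confirmation sentences in IV.a and IV.d could mean that culture decides the case. IV.e brings in history and complaints as well as culture. None of them says whether a positive culture without symptoms overrides the adjudication criterion.

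**What does the planning rate count?** IV.b plans on 40%, referring back to a rate given earlier, and section II gives near 40% without saying what is counted. The Discomforts paragraph under Anticipated Risks in IV.e describes a rate as high as 40% as symptomatic plus asymptomatic UTI, and presents it as already discussed. That links the planning figure to the broader definition.

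**Is the sample size itself in error?** No. With 40% v 20%, 100 per arm, two-sided 0.05 (sidedness is not stated, so this is assumed) and a continuity correction of 1/n, power is Φ[(0.20 − 0.01 − 1.96 × √(2 × 0.30 × 0.70/100)) / √((0.24 + 0.16)/100)] = Φ[(0.19 − 0.127)/0.0632] = Φ(0.996) = 0.84, as IV.b states.

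**The case against.** The strongest reply is that the intent can be recovered. The asymptomatic sentence is express and is framed as a rule for this study, while the conflicting words are only a gloss in parentheses. Since asymptomatic bacteriuria is the only kind defined by name above, the back-reference itself suggests a slip. The 40% rate under Anticipated Risks covers both kinds. The emergency department sentence concerns those reports only and does not narrow the endpoint. All of this stands, and it makes the broader definition the better-supported reading. It does not put that reading into the text the adjudicators will follow.

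A second reply is that few patients may be affected. Positive samples go to the hospital laboratory under usual procedures, and IV.e foresees that an abnormal sample may lead to treatment. Some symptom-free patients may therefore acquire a chart diagnosis and never reach adjudication. Treated patients with neither laboratory evidence nor a chart diagnosis may be very few. This also stands: the documents do not size either group.

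A reader might infer that the trial will lose events and therefore power. The documents do not support this. If *symptomatic* is a slip, or if culture settles the case, no culture-positive patient is lost. On the literal reading the loss depends on the asymptomatic share, which is not given. Nor do they support the inference that the endpoint was meant to be symptomatic only. The adjudication rule is the same for both arms, so the wording conflict alone does not show a bias between them.

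**Conclusion.** The conflict is real and should be fixed before endpoints are classified. IV.a contains two incompatible rules for the primary endpoint. The adjudication rule, followed as written, rejects patients whom the section expressly counts. This is more than missing detail, because a stated rule gives the wrong classification under another stated rule.

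Confidence is high on the wording conflict and does not extend to any consequence for the results. The number of patients affected and any loss of power cannot be determined from the documents. The conclusion rests on one practical assumption: that at least some patients who meet an inclusion rule will have no UTI diagnosis in the outside chart. The research-only samples make that foreseeable.

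**What to change.** Replace the parenthesis in the adjudication sentence with a reference to the study's own definition, for example: *meeting the study's UTI criteria above, including asymptomatic bacteriuria (culture above 10^5 CFU/mL) and antibiotic treatment for UTI with no laboratory support*. Re-read under the agreed wording any cases that have already been adjudicated; the documents do not show whether there are any.

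If symptomatic cases only were intended, the asymptomatic sentence has to be changed instead, and the 40% planning rate reconsidered, since Anticipated Risks describes it as covering both kinds.

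No further endpoint rules are needed to resolve the conflict. The cost is one amended sentence, plus the re-read if it applies. No new samples or visits are required, because laboratory confirmation and culture are already planned.
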